4.4.2 Other Safety Evaluation Parameters

4.4.2.1 Slit Lamp Examination

External ocular examination and undilated biomicroscopy will be performed using a slit lamp at each scheduled visit. Grading of the Meibomian glands, conjunctival erythema, anterior chamber inflammation, lens, and vitreous will be on a 0 to 3 scale; 0 indicates normal and 3 indicates the most severe state. Lid erythema, lid oedema, conjunctival oedema, and tear film debris will be graded on a 0 to 4 scale; 0 indicates normal and 4 indicates the most severe state. Lashes will be graded as normal or abnormal (Appendix A).

A decrease in slit lamp grading indicates an improvement in the slit lamp finding.

4.4.2.2 Uncorrected Distance Visual Acuity (UDVA)

UDVA will be measured on LogMAR scale at each scheduled visit and at the premature study discontinuation visit.

A decrease in LogMAR UDVA indicates improvement in the uncorrected distance visual acuity.

4.4.2.3 Best-Corrected Distance Visual Acuity (BCDVA)

BCDVA measures the acuteness or clearness of best-corrected distance vision. It will be measured on LogMAR scale at each scheduled visit and at the premature study discontinuation visit.

A decrease in LogMAR BCDVA indicates improvement in the best-corrected distance visual acuity.

4.4.2.4 Dilated Fundus Examination

A dilated fundus examination will be performed after the pupil is dilated at the Baseline and Month 3/early termination visits in order to evaluate for posterior segment diseases. It will be rated as normal or abnormal.

4.4.2.5 Intraocular Pressure (IOP)

IOP will be measured using Goldman applanation tonometry (one measurement) at the Baseline and Month 3/early termination visits.

A decrease in IOP indicates improvement in the intraocular pressure.

4.5 Other Definitions

4.5.1 **Prior and Concomitant Medications**

Non-study medications will be categorized into prior medications and concomitant medications. Specifically, *prior medication* is defined as any non-study medication taken and ended prior to the treatment start date. *Concomitant medication* is defined as any non-study medication taken concurrently while on the study medication.

All prior and concomitant medications will be coded using the World Health Organization Drug Dictionary Enhanced (WHO-DDE), Format C English, March 2016. Each prior or concomitant medication will be classified using the Anatomical-Therapeutic-Chemical (ATC) classification system and mapped to a WHO-DDE preferred drug name.

4.5.2 Concurrent Medical Conditions

Concurrent medical conditions are those significant ongoing conditions or diseases that are present at signing of informed consent.

4.5.3 Treatment Compliance

Compliance to the study medication use is tracked on the Compliance eCRF as the number of single dose medication containers dispensed at the beginning of the study period plus the number of single dose containers dispensed at any unscheduled visit during that period, and the number of used and unused containers returned or not returned at the following visit (including unscheduled visits). For the purpose of treatment compliance calculation, there will be three study periods:

- Baseline Visit (Day 1) to Month 1 Visit
- Month 1 Visit to Month 2 Visit
- Month 2 Visit to Month 3 Visit

For a given study period, compliance rate is calculated using the following formula, which assumes that the unreturned bottles are not used:

Compliance =
$$\frac{\text{Number of containers used}}{\text{Number of days of the follow-up interval}} \times 100$$

= $\frac{\text{Number of USED containers returned}}{\text{Date of current visit} - \text{Date of preceding visit}} \times 100$

Compliance rate of $\geq 80\%$ will be treated as compliant.

For subjects who did not return their used and/or unused bottles at the next visit, that patient will be treated as 100% compliant if the site could confirm that the patient was compliant during the preceding month.

5 STUDY POPULATION

5.1 Full Analysis Set

The *Full Analysis Set* (FAS) includes all enrolled subjects who received at least one dose of the study medication. This will be the population used for efficacy analyses.

5.2 Safety Population

The *Safety* population will include all enrolled subjects who received at least one dose of the study medication and for whom any follow-up information is available. It will be the analysis population for safety analyses.

5.3 **Per-Protocol Population**

The *Per-Protocol* (PP) population will be a subset of the FAS subjects. It includes all FAS subjects without any of the following protocol deviations that could affect the primary efficacy endpoint.

- Failing to fulfill certain inclusion/exclusion criterion(a)
- Has a significant protocol deviation that could alter his/her efficacy outcome to treatment
- Without the primary efficacy measures of CFS, VMR, and OSI at the Month 3 visit
- Other significant protocol deviations identified by Santen's study team

Santen's study team will review all protocol deviations and identify subjects to be excluded from the PP population before the database lock.

6 GENERAL CONSIDERATIONS

Statistical analyses will be performed based on this SAP by the Biometry Unit of Euraxi, a contract research organization (CRO) based in Joué Les Tours, France.

Unless specified otherwise, all efficacy analyses will be performed using data from the analysis eye of FAS subjects, and all safety variables will be analyzed separately for both the analysis eyes and the fellow eyes on the Safety population.

Continuous variables will be summarized using descriptive statistics such as number of observations (n), mean, standard deviation, median, minimum, and maximum. Categorical variables will be tabulated using frequency (n) and percent (%).

All statistical testing will be conducted at a significance level of 0.05 (two-sided) unless specified otherwise. No statistical testing will be conducted for safety measures.

All data manipulations, descriptive summaries, and statistical testing will be performed using SAS Version 9.4 or later.

6.1 Adjustments for Covariates

Details on covariates to be included in the statistical model for each individual statistical analysis are provided in Section 8.1.2.

6.2 Handling of Missing Data

6.2.1 Efficacy Endpoints

Missing observations on CFS, VMR, and variance of OSI will be imputed by the last-observation-carried-forward (LOCF) approach.

6.2.2 Safety Endpoints

Descriptive summaries of safety measures will be based on observed data only. No imputation of missing scores will be implemented.

6.2.3 Dates for Medical Events and Medications

Completely or partially missing onset and/or resolution dates for medical events (including AEs, medical history, and concomitant medications) will be imputed in a conservative fashion as follows:

Date	Type of Missing Date	Handling of Missing Date
Event onset date	Completely missing	No imputation will be applied.
(e.g., YYYY-MM- DD)	Only YYYY is available	Use the first day of YYYY to impute the missing month and date parts of the onset date

	YYYY and MM are available but DD is missing	Use the first day of MM to impute the missing date part of the onset date
Event resolution date (e.g., YYYY-MM- DD)	Completely missing	No imputation will be applied. The event will be considered ongoing (i.e., not resolved) at the last visit date.
	Only YYYY is available	Use the last day of YYYY to impute the missing month and date parts of the resolution date
	YYYY and MM are available but DD is missing	Use the last day of MM to impute the missing date part of the resolution date

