## 12.6 AEs

Adverse events will be coded using the MedDRA dictionary. Frequencies and percentages will be provided of patients with treatment-emergent adverse events (TEAEs), serious TEAEs, and TEAEs causing premature discontinuation. An adverse event is treatment emergent if it occurs or worsens after the first dose of study treatment. Furthermore, frequencies will be given of patients with TEAEs as follows: 1) by system organ class, by system organ class and preferred term, 2) by system organ class, preferred term and maximal severity, 3) by system organ class, preferred term and strongest relationship, and 4) by system organ class, preferred term, maximal severity, and strongest relationship.

Separate analyses will be performed for ocular and systemic adverse events. Ocular AEs will be summarised for the analysis eye and the other eye separately.

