4.4 Safety-Related Definitions

4.4.1 Adverse Event (AE)

Events reported on the AE electronic case report form (eCRF) will be assessed according to the amended FDA regulations 21 CFR Parts 312 and 320.

Under Protocol NVG16E128, an AE is defined as any untoward medical occurrence in a clinical investigation patient administered an investigational product; it does not necessarily have to have a causal relationship with the treatment. An AE will be considered as a *pre-treatment event* (PTE) if the AE occurred after the patient has signed informed consent to participate in the study but prior to administration of any study medication; it does not necessarily have to have a causal relationship with study participation. An AE will be considered as *treatment-emergent* if the AE occurred on or after the treatment start date up to the last study visit or worsened relative to pre-treatment state.

The severity of each AE will be graded by the Clinical Investigator as Mild (aware or unaware of event, but easily tolerated), Moderate (discomfort enough to cause interference with usual activity), or Severe (incapacitating; unable to work or perform usual activity). AEs will also be rated by the Investigator as to their causality/relationship to the study medication, to the Sponsor provided artificial tears, as well as to the study procedures (related vs. not related).

Each AE will be classified into a system organ classification (SOC) and coded to a preferred term (PT) using Medical Dictionary for Regulatory Activities (MedDRA, version v19.1 English, March 2016).

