9 SAFETY ANALYSES

The safety-related measures collected in this study include systemic and ocular AEs, corrected and uncorrected distance visual acuity, slit-lamp biomicroscopy, dilated fundus examinations, and IOP. The Safety population will be used for all safety summaries.

All the safety-related measures will be summarized descriptively. Except systemic AEs, which will be summarized at the subject level, all the other safety-related measures, including ocular AEs, will be summarized for the analysis eyes and fellow eyes separately.

9.1 **Pre-treatment Events (PTEs) and Adverse Events (AEs)**

PTEs and AEs are defined in Section 4.4.1. PTEs and treatment-emergent AEs (TEAEs) will be summarized separately.

In the overall AE summaries, subjects with any AE(s) will be tabulated by the following types of AEs:

- AEs
- SAEs
- Related AEs
 - AEs related to the study medication
 - AEs related to artificial tears
 - AEs related to study procedures
- AEs leading to premature discontinuation
- Sight threatening AEs
- Case of special interest
- Death

The above summaries will be repeated for ocular AEs in the analysis eye, ocular AEs in the fellow eye, and non-ocular AEs, respectively.

Besides the overall AE summaries listed above, AEs will be tabulated by SOC and PT. A subject who experienced multiple AEs within a SOC or PT will be counted only once for that SOC or PT, respectively. SAEs, related AEs, and serious related AEs will be tabulated similarly. Ocular and systematic AEs will also be summarized separately.

In addition, AEs will be tabulated by the following categories:

- SOC, PT, and maximal severity
- SOC, PT, and relationship (related to study medication, study procedure, or artificial tears)
- SOC, PT, maximal severity, and relationship (related to study medication, study procedure, or artificial tears)

Ocular AEs will be summarized for the analysis eye and fellow eye separately. Any ocular AE that occurred simultaneously to both eyes will be counted once for both the analysis eye and the fellow eye. Sight-threatening AEs and cases of special interest will be summarized by type of events specified in Section 4.4.1.2 and Section 4.4.1.3.

AEs, AEs leading to discontinuation, SAEs, sight-threatening AEs, case of special interest, and death, if any, will be listed separately.

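### Partly missing AE onset dates are imputed without reference to first dose, so some new on-treatment events are dated before dosing and not counted as treatment-emergent

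*SAP*

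**What the plan says.** SAP 6.2.3 has one rule for incomplete dates of AEs, medical history and medications, which "will be imputed in a conservative fashion as follows". For an onset with month and year known: "Use the first day of MM to impute the missing date part of the onset date". For an onset with only the year known: "Use the first day of YYYY to impute the missing month and date parts of the onset date". A fully missing onset is not imputed. Partial resolution dates go to the last day of the known month or year.

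SAP 4.4.1 calls an AE treatment-emergent if it "occurred on or after the treatment start date up to the last study visit or worsened relative to pre-treatment state". It calls an AE a pre-treatment event (PTE) if it "occurred after the patient has signed informed consent to participate in the study but prior to administration of any study medication".

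The classification drives the tables. In SAP 9.1, "PTEs and treatment-emergent AEs (TEAEs) will be summarized separately". Protocol 12.6 plans: "Frequencies and percentages will be provided of patients with treatment-emergent adverse events (TEAEs), serious TEAEs, and TEAEs causing premature discontinuation".

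**The concern.** The imputation has no floor at the first-dose date, and neither document overrides it for an onset in the month or year of first dose. A new event that began after dosing can therefore be given an onset before dosing. The worsening limb of the TEAE definition does not rescue it, because a new event has no pre-treatment state to worsen from.

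The error runs one way: first-day imputation can move an on-treatment event out of the TEAE count but cannot move a pre-treatment event in. What is at stake is TEAE incidence, including the serious and discontinuation rows of Protocol 12.6. A fully missing onset has no defined status at all.

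**Working it through.** The documents give no figure to reproduce: neither states a rate of partial dates or an expected TEAE count.

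**Example.** First dose 15 March, new event 20 March.
- Day missing: onset becomes 1 March, not a TEAE.
- Year only: onset becomes 1 January, not a TEAE.
- Had the event begun on 10 April with the day missing, it would become 1 April and remain a TEAE.

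**Inputs.** Treatment runs 84 days, with 77 and 91 as limits (Day 84 ± 7, Protocol 2.0). Consent is taken as 14 days before first dose (Screening visit at Day -14). Assumptions: first-dose dates uniform over a 365-day year, and onset uniform over treatment.

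**Day missing.** In a month of n days, a start on day d (d ≥ 2) puts n − d + 1 on-treatment days in the first-dose month, and all of them are dated before dosing. Summed over d this is n(n − 1)/2.
- Year total: 7 × 465 + 4 × 435 + 378 = 5,373. Mean per start date: 5,373/365 = 14.72 days.
- 14.72/84 = 17.5%; 14.72/77 = 19.1%; 14.72/91 = 16.2%.
- All of these fall in study days 1 to 30: 14.72/30 = 49% there, and 0% from day 31.
- Dated before consent (d ≥ 16): (n − 15)(n − 14)/2 per month, so 7 × 136 + 4 × 120 + 91 = 1,523; 1,523/365 = 4.17 days; 4.17/84 = 5.0%. The other 12.6% are dated in the PTE period.
- 1/0.1752 = 5.7, so about six day-missing on-treatment AEs are needed to expect one misplacement.

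**Year only.** Every on-treatment day in the first-dose year is lost, unless dosing began on 1 January.
- 84 days: 84 × 365 = 30,660 start-by-onset pairs. Subtract 3,486 falling in the next year and 84 for a 1 January start: 27,090/30,660 = 88.4%.
- Study days 31 to 84: (54 × 365 − 3,051 − 54)/19,710 = 16,605/19,710 = 84.2%.

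**Wash-out onsets, day missing, 14 days.** Per start date:
- 3,850/365 = 10.55 days fall in the first-dose month. Of these, 2,590/365 = 7.10 are imputed to before consent.
- The other 14 − 10.55 = 3.45 days fall in the previous month, and all are imputed to before consent.
- Total dated before consent: 7.10 + 3.45 = 10.55.

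**Onset-days in the wrong category**, at equal daily event rates before and after dosing:
- Current rule: 14.72 on-treatment + 10.55 wash-out = 25.3.
- Treatment-start rule without a consent floor, where f is the share of wash-out events not recorded by Baseline: 10.55f + 7.10(1 − f) + 3.45. This gives 14.0 (f = 1), 12.3 (f = 0.5) and 11.4 (f = 0.25).

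**One patient.** SAP 3.1 reports 17 enrolled. If all were treated and the event is that patient's only one in a row, the row changes by 1/17 = 5.9 percentage points.

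**The case against.** **Partial dates should be rare.** Protocol 10.2.1.2 requires start and stop dates, visits are about monthly, and Protocol 11.1 queries missing data. This stands and limits the importance of the point. The SAP nevertheless plans for partial dates, so its rule should work when one occurs.

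**The documents never say that the imputed date decides status.** Protocol 10.2.1.1 separates PTE and AE collection at first dose, and Protocol 10.2.1.2 leaves drug causality and action taken blank for PTEs, so the site record might show the true timing. But the SAP does not say it will use that record, and the record is not clean. Protocol 9.3.5.6 and 9.3.5.7 report wash-out changes as AEs, and SAP 4.4.1 says "AEs will also be rated by the Investigator as to their causality/relationship to the study medication" without exempting PTEs. A completed causality or action field can support on-treatment onset; a blank one may be missing data.

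**The rule is conservative.** It is, for event duration and medication overlap. It is anti-conservative only for TEAE status, so a reader should not infer that it is wrong for every use.

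**Stronger readings that the documents do not support.**
- A reader might infer that events dated before consent vanish from the report. They meet neither the PTE nor the TEAE definition, but they stay in the AE listings and possibly in SAP 9.1 rows not expressly limited to TEAEs.
- A reader might infer that only the first 30 study days are exposed. That holds for day-missing dates, not for year-only dates.
- A reader might infer that the safety findings are materially biased. Without a count of partial dates this cannot be said. SAP 6 plans no safety testing, and serious PTEs still count as SAEs (SAP 4.4.1.1).

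**Conclusion.** The point holds as a minor correction. As written, the rule removes from the TEAE count new on-treatment AEs with a partial onset in the month or year of first dose, unless dosing began on the first day of that month or year.

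The percentages above describe partially dated events only, not all AEs, and rest on uniform start and onset dates. The number of events affected depends on how many dates are partial, which the documents do not give. No efficacy result is touched. The 5.9-point figure would be slightly larger if fewer than 17 patients were treated, since enrolment precedes the wash-out and the eligibility check.

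**What to change.** Add one paragraph to SAP 6.2.3, for AEs only, before database lock:

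1. If month and year are known and match those of first dose, or only the year is known and it matches, impute the treatment start date. Otherwise keep the first-day rule.
2. Make two exceptions: the resolution date, after its own last-day imputation, precedes first dose; or the data show that the event was recorded at or before the Baseline visit. Use the second only if the eCRF captures when an event was recorded, because the per-event items in Protocol 10.2.1.2 do not include it.
3. Treat a fully missing onset as treatment-emergent under the same exceptions.
4. Let a completed drug-causality or action-taken field support on-treatment onset. Do not let a blank field alone establish pre-treatment onset.
5. Do not impute the onset of an event classed as a PTE to before the consent date.

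Keep the current rule for medical history and medications.

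The cost is that some partially dated wash-out events may be counted as TEAEs, an error in the conservative direction. If the eCRF does not capture when events were recorded, f = 1 applies: 14.0 misplaced onset-days against 25.3 now. The consent floor in item 5 addresses the part of the remainder that comes from wash-out events dated before consent.

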6.3 Multi-Center Studies

This is a multi-center study enrolling subjects from approximately 4 France centers. Sites will not be pooled into any subgroups for any inferential analysis. Sites will be included as a covariate in the mixed-effects model for repeated measures (MMRM) analysis.

6.4 Multiple Comparisons / Multiplicity

Since the FAST study is a proof-of-concert study and considered as purely exploratory, no multiplicity adjustment will be conducted to control the overall Type I error rate.

6.5 Interim Analysis

No formal interim analysis is planned for this study.

7 SUMMARY OF STUDY POPULATION DATA

7.1 Subject Disposition

The subject disposition for all enrolled subjects will be tabulated by study population and completion status at Month 3. Subjects who discontinued the study before Month 3 will be tabulated by the primary discontinuation reason. In addition, the subject enrollment will be summarized by site.

7.2 Demographics and Baseline Characteristics

Subject demographics and baseline characteristics will be descriptively summarized for all FAS subjects. Specifically, for subject demographics, the following variables will be summarized:

- Age at enrollment (continuous and categorical: < 65 years, ≥ 65 years)
- Gender (male, female)
- For female patients, contraception and pregnancy avoidance procedure (confirmed menopause, effective contraception, none)

For baseline characteristics, the following variables will be summarized:

- Alcohol use [≤ 30 g per day (women) or ≤ 40 g per day (men), > 30 g per day (women) or > 40 g per day (men)]
- Illicit or recreational drug use (yes, no)
- Tobacco use
 - o Yes
 - Ex-smoker (number of packets per year, duration of smoking, duration of quitting smoke)
 - Current smoker (number of packets per year, duration of smoking)
 - o No
 - Passive tobacco use (yes, no)

7.3 Medical and Surgical History

The medical and surgical history (i.e., medical events) will be coded using MedDRA (version v19.1 English, March 2016) and summarized for the FAS population. Each medical event will be classified into a system organ class (SOC) and mapped to a preferred term (PT). Any subject with more than one medical and/or surgical term within the same SOC or mapped to the same PT will be counted only once for that SOC or PT.

7.4 **Protocol Deviations**

In this study, protocol deviations are categorized as follows:

- Safety issues
 - Study drug storage condition outside of the protocol-defined condition

- Consent issues
 - Informed consent not signed
 - Informed consent data missing or not available
- Enrollment issues
 - Ineligible subject enrolled
- Protocol implementation issues
 - Visit out of window
 - Protocol-required exam(s) not done or missing
 - Administered rescue medication/therapy
 - Used prohibited medications/therapy
 - Non-compliance (compliance rate < 80%)
- Other

A protocol deviation is considered major if it may affect the subject's rights, safety, or wellbeing and/or the completeness, accuracy, and reliability of the study data. Santen's study team will review all protocol deviations and determine the list of major protocol deviations prior to database lock. FAS subjects with any major protocol deviation(s) will be tabulated by deviation category. In addition, protocol deviation(s) will also be listed.

